#### **Elevation of Either ALT or AST to $\geq 3 \times$ ULN**

Confirmation is required prior to IMP discontinuation in cases of elevation of either ALT or AST  $\geq 3 \times$  ULN. (Note: In cases of elevation of ALT or AST  $\geq 8 \times$  the ULN, no confirmation is required prior to IMP discontinuation, but the assessments below should be performed.) The following procedures should be followed:

- The day in which the abnormal value is received from the laboratory will be considered as day 0.
- The investigator should repeat the test for confirmation purposes (this may be performed in a local laboratory along with complete blood cell [CBC] count and differential to assess for eosinophilia; in general, in case a blood sample is sent to a local laboratory, the following assessments [and reference ranges] are mandatory: ALT [serum glutamic pyruvic transaminase], AST [serum glutamic oxaloacetic transaminase], ALP, bilirubin [total, direct, and indirect], CBC [with differential for eosinophil count, separate tube], and INR [separate tube; not to be sent in a confirmatory test]). The investigator should also question the patient regarding symptoms.

The abnormality will be regarded as confirmed in each of the following scenarios:

- the baseline value was within the normal range and ALT or AST is still  $\geq 3 \times$  the ULN
- the baseline value was above the ULN and ALT or AST is  $\geq 2 \times$  the baseline value

---

 Thorough medical history with a focus on liver disease: personal or family history of liver disease; personal history of a systemic disease with potential liver involvement; exposure to alcohol, medications (prescription or over-the-counter), herbal preparations, dietary supplements, recreational drugs, special diets, or environmental chemical agents; potential exposure to infectious agents (eg, travel to developing countries, history of potential exposure to blood or blood products, high-risk sexual relations); and any additional information deemed relevant by the investigator. Physical examination, including signs of chronic liver disease.

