**Additional Tests/Evaluations:**

Upon confirmation of the abnormality as noted above, the following additional evaluations should be performed and results should be recorded in the CRF:

- serology for hepatitis A (antibody and immunoglobulins M and G), B (core antibody total, core immunoglobulin M, and surface antigen), and C viruses (central laboratory)
- serology for autoimmune hepatitis: anti-nuclear antibodies (titer), anti-smooth muscle antibodies, and anti-liver kidney microsomal antibodies (central laboratory); further testing may be required in case of a positive result for hepatitis B or C
- ultrasound examination of the liver and biliary tract at the investigator's discretion
- other diagnostic tests/consultations as deemed necessary by the investigator (eg, serology for hepatitis E virus in case of travel to endemic geography)
- observation and follow-up (to be performed after the abnormality was confirmed as above)

**ALT or AST  $\geq 3 \times$  ( $>3.5 \times$  the ULN if the Baseline Value is  $>2.5 \times$  the ULN) but  $<5 \times$  the ULN**

In addition to the above procedures required for any elevation to levels  $>3 \times$  the ULN:

- Alanine aminotransferase, AST, GGT, ALP, total bilirubin, direct bilirubin, indirect bilirubin, CBC and differential (to assess for eosinophilia), and INR should be monitored on days 5 ( $\pm 2$  days), 8 ( $\pm 2$  days), 14 ( $\pm 3$  days), and 28 ( $\pm 3$  days). On at least 1 of these days, the test should be performed centrally. (The INR should be sent to a local laboratory only.)
- In cases where a local laboratory is used, the results should be recorded in the CRF, accompanied by the reference range of the relevant measurements.
- Should the abnormality ( $\geq 3 \times$  the ULN in case baseline was within the normal range or  $\geq 2 \times$  the ULN in case the baseline value was above ULN but still  $<5 \times$  the ULN) persist further, the patient will be followed according to the investigator's discretion, but a blood sample for ALT, AST, GGT, ALP, and total bilirubin, direct bilirubin, indirect bilirubin should be sent to the central laboratory at least once a month.

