**Stopping Rules**

In the following circumstances, the IMP will be discontinued immediately:

- any increase in ALT or AST to  $\geq 3 \times$  the ULN, combined with INR  $>1.5 \times$  the ULN or total bilirubin  $>2 \times$  the ULN
- any increase in ALT or AST to  $\geq 3 \times$  the ULN, which is accompanied by symptoms clearly associated with impaired liver function (eg, vomiting, nausea, fever, rash, and eosinophilia) and not deemed related to other diseases (eg, vomiting or nausea triggered by cluster headache)
- any increase in ALT or AST to levels  $\geq 5$  but  $<8 \times$  the ULN, which is persistent for  $\geq 2$  weeks of repeated measurements
- any increase in ALT or AST to levels  $\geq 8 \times$  the ULN
- in any case where monitoring of liver enzymes cannot be performed according to the protocol guidance

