**Follow-Up of Liver Enzymes After Stopping Rules Are Met**

- A patient who meets the above criteria for discontinuation of the IMP should be invited to the investigational site to return the IMP. Early withdrawal visit activities should be performed as soon as possible.
- Liver enzymes should be monitored until normalization or stabilization of the abnormality, according to the discretion of the investigator.
- In any case, following the early withdrawal visit, the minimal follow-up period will be 30 days and will include measurement of liver enzymes at least once weekly (may be performed in local laboratory, with at least 1 test being sent to the central laboratory).
- Every effort should be made to complete the additional tests/evaluations, as described above.

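### Appendix J gives conflicting orders for ALT or AST of 3 to <8 × ULN with total bilirubin >2 × ULN, INR >1.5 × ULN or hepatic symptoms: confirm before stopping, and stop at once

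*Protocol*

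**What the plan says.** Three parts of Protocol Appendix J bear on this point.

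- **Elevation of Either ALT or AST to ≥3 × ULN.** "Confirmation is required prior to IMP discontinuation in cases of elevation of either ALT or AST" at this level. One exception is written: at 8 × ULN or more, "no confirmation is required prior to IMP discontinuation, but the assessments below should be performed". The repeat counts as confirmation if ALT or AST is still at least 3 × ULN (normal baseline), or at least 2 × the baseline value (baseline above ULN). Bilirubin is in the mandatory panel if a local laboratory is used, but plays no part in the criterion. INR is "not to be sent in a confirmatory test".
- **Stopping Rules.** "In the following circumstances, the IMP will be discontinued immediately". The list includes any rise to at least 3 × ULN combined with INR >1.5 × ULN or total bilirubin >2 × ULN, and any rise to at least 3 × ULN "which is accompanied by symptoms clearly associated with impaired liver function". No confirmation step is mentioned for either.
- **What follows each route.** Under Additional Tests/Evaluations the work-up depends on the repeat: "Upon confirmation of the abnormality as noted above, the following additional evaluations should be performed". Under Follow-Up of Liver Enzymes After Stopping Rules Are Met, the early withdrawal visit is done as soon as possible, "the minimal follow-up period will be 30 days and will include measurement of liver enzymes at least once weekly", and "Every effort should be made to complete the additional tests/evaluations, as described above".

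Sections 3.4 and 4.3 only refer back to Appendix J.

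**The concern.** A site holding a first result of, say, ALT 4 × ULN with bilirubin 2.5 × ULN has two instructions. One section tells it to repeat the test before discontinuing; the other tells it to discontinue now. No sentence ranks them.

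These are the combined liver signals for which the protocol itself wants an immediate stop. The choice of reading affects more than timing, because it also decides whether the early withdrawal visit, the weekly liver tests and the aetiological work-up are triggered. Sites could manage identical patients differently while each follows the text.

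**Working it through.** The plan states no figure to reproduce, so the check sets the rules side by side and then works two illustrative patients.

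**Rules by band**

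| ALT or AST | Accompanying finding | ≥3 × ULN section | Stopping Rules | Consistent? |
|---|---|---|---|---|
| ≥8 × ULN | any | no confirmation needed | stop immediately | yes |
| ≥5 to <8 × ULN | persists ≥2 weeks | repeat testing | stop after repeated measurements | yes |
| ≥3 to <8 × ULN | bilirubin >2 × ULN or INR >1.5 × ULN | confirm first | stop immediately | **no** |
| ≥3 to <8 × ULN | hepatic symptoms | confirm first | stop immediately | **no** |
| ≥3 to <8 × ULN | none, not persistent | confirm | no rule met | yes |

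The conflict is confined to the third and fourth rows.

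**Confirmation threshold**

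- Normal baseline: 3.0 × ULN.
- Baseline 1.2 × ULN: 2 × 1.2 = 2.4 × ULN.
- Baseline 1.5 × ULN (the limit in exclusion criterion q, Section 4.2): 2 × 1.5 = 3.0 × ULN.

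**Patient A** (assumed values): normal baseline; first ALT 4 × ULN, bilirubin 2.5 × ULN; repeat ALT 2.8 × ULN, bilirubin unchanged.

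- Stopping Rules: 4 ≥ 3 and 2.5 > 2, so stop at the first result. Early withdrawal visit, additional tests, and 30/7 = 4.3, that is at least 4 weekly liver tests.
- ≥3 × ULN section: 4 < 8, so not exempt. Repeat 2.8 < 3.0, so not confirmed. The precondition for stopping is unmet and the additional work-up is not triggered. The liver-focused history and examination still apply, since 2.8 ≥ 2.

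**Patient B**: same values, but baseline ALT 1.2 × ULN. Repeat 2.8 ≥ 2.4, so confirmed. The two sections now differ only by the time the repeat takes.

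**The INR criterion.** Because INR is left out of the confirmatory sample, the repeat cannot recheck a stop triggered by INR.

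**Room for a further dose.** The IMP is given at weeks 0, 4 and 8. Among scheduled on-treatment samples, only week 4 precedes another dose in this study. With the Table 2 windows (day 28 ± 3, day 56 ± 3), the gap is 53 − 31 = 22 days at least and 59 − 25 = 34 days at most.

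**The case against.** The best defence is that the sections run in sequence: the first verifies the laboratory value, and the Stopping Rules say how fast to act once a criterion is established. In support, the word for immediate action also governs the limb requiring two weeks of repeated measurements, so it need not mean action on the first result. The repeat visit also collects bilirubin, eosinophils and symptoms, which the Stopping Rules use, and Section 7.4 speaks of abnormalities confirmed by repeat testing that lead to withdrawal.

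This does not remove the conflict. The Stopping Rules write repeated measurements into the one limb where they want them and omit them from the combined criteria. The ≥8 × ULN case is also a stopping rule, yet the drafters gave it an express exemption from confirmation. Naming only that case implies that the others still need the repeat. Section 7.4 is adverse-event recording text. And under confirm-then-stop, Patient A's bilirubin can stay above 2 × ULN while the ALT criterion is never confirmed.

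The argument about consequences does stand. There is no IMP to stop between visits, the repeat can be done locally, and a half-life of 32.2 to 36.2 days (Section 1.2.2.1) means a few days' delay barely changes exposure. A site unable to carry out the required monitoring must stop under the last stopping rule. Once an elevation is confirmed, INR is monitored, from day 5 or twice weekly depending on the band.

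**Conclusion.** The inconsistency is real and the effect is minor. It covers only ALT or AST of 3 to <8 × ULN with total bilirubin >2 × ULN, INR >1.5 × ULN or hepatic symptoms. Isolated elevations, the two-week persistence rule and values of 8 × ULN or more are handled coherently.

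Harm is limited in several ways. Section 4.3 provides for withdrawal on the investigator's judgement or at the sponsor's request. These values are events of special interest (Section 7.1.7), reported within 24 hours by the serious adverse event route (Section 7.1.5.3.1). Appendix J asks for a liver-focused history and examination at 2 × ULN without confirmation, and a result judged clinically significant is followed as an adverse event (Sections 7.1.2 and 7.4).

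The documents give no rate for these events. Section 1.2.2.2 reports no clinically relevant laboratory changes to date, so few patients are expected. Patients A and B are constructed to show where the rules part and are not forecasts. No efficacy or safety analysis changes.

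**What to change.** Extend the existing note in the ≥3 × ULN section so that it covers two cases: ALT or AST of 8 × ULN or more, and ALT or AST of at least 3 × ULN meeting the bilirubin, INR or symptom criterion in the Stopping Rules. The rest of the note stays as it is: "no confirmation is required prior to IMP discontinuation, but the assessments below should be performed".

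This uses the appendix's own exemption and keeps confirmation for isolated elevations. Adding a confirmation requirement to the Stopping Rules would also make the text consistent, but it would leave Patient A's stop unauthorised while bilirubin remains raised.

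The cost is one sentence, by written amendment if Appendix C requires it, with no new tests, visits or dosing changes. The downside is an occasional discontinuation that a repeat might have averted, which the Stopping Rules as written already accept.

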**Additional Tests/Evaluations:**

Upon confirmation of the abnormality as noted above, the following additional evaluations should be performed and results should be recorded in the CRF:

- serology for hepatitis A (antibody and immunoglobulins M and G), B (core antibody total, core immunoglobulin M, and surface antigen), and C viruses (central laboratory)
- serology for autoimmune hepatitis: anti-nuclear antibodies (titer), anti-smooth muscle antibodies, and anti-liver kidney microsomal antibodies (central laboratory); further testing may be required in case of a positive result for hepatitis B or C
- ultrasound examination of the liver and biliary tract at the investigator's discretion
- other diagnostic tests/consultations as deemed necessary by the investigator (eg, serology for hepatitis E virus in case of travel to endemic geography)
- observation and follow-up (to be performed after the abnormality was confirmed as above)

**ALT or AST  $\geq 3 \times$  ( $>3.5 \times$  the ULN if the Baseline Value is  $>2.5 \times$  the ULN) but  $<5 \times$  the ULN**

In addition to the above procedures required for any elevation to levels  $>3 \times$  the ULN:

- Alanine aminotransferase, AST, GGT, ALP, total bilirubin, direct bilirubin, indirect bilirubin, CBC and differential (to assess for eosinophilia), and INR should be monitored on days 5 ( $\pm 2$  days), 8 ( $\pm 2$  days), 14 ( $\pm 3$  days), and 28 ( $\pm 3$  days). On at least 1 of these days, the test should be performed centrally. (The INR should be sent to a local laboratory only.)
- In cases where a local laboratory is used, the results should be recorded in the CRF, accompanied by the reference range of the relevant measurements.
- Should the abnormality ( $\geq 3 \times$  the ULN in case baseline was within the normal range or  $\geq 2 \times$  the ULN in case the baseline value was above ULN but still  $<5 \times$  the ULN) persist further, the patient will be followed according to the investigator's discretion, but a blood sample for ALT, AST, GGT, ALP, and total bilirubin, direct bilirubin, indirect bilirubin should be sent to the central laboratory at least once a month.

**ALT or AST  $\geq 5 \times$  but  $<8 \times$  the ULN**

In addition to the above procedures required for any elevation to levels  $>3 \times$  the ULN:

- Alanine aminotransferase, AST, GGT, ALP, total bilirubin, direct bilirubin, indirect bilirubin, CBC and differential count (to assess for eosinophilia), and INR should be monitored twice a week.
- At least for every other measurement, the tests should be sent to the central laboratory. The rest of the tests may be sent to a local laboratory. The INR should always be sent to a local laboratory.

**ALT or AST  $\geq 8 \times$  the ULN**

In addition to the above procedures required for any elevation to levels  $>3 \times$  the ULN:

- The IMP should be discontinued immediately, and the early withdrawal visit should be performed.
- For follow-up guidance, please see below section “Follow-Up of Liver Enzymes after Stopping Rules Are Met.”

**Stopping Rules**

In the following circumstances, the IMP will be discontinued immediately:

- any increase in ALT or AST to  $\geq 3 \times$  the ULN, combined with INR  $>1.5 \times$  the ULN or total bilirubin  $>2 \times$  the ULN
- any increase in ALT or AST to  $\geq 3 \times$  the ULN, which is accompanied by symptoms clearly associated with impaired liver function (eg, vomiting, nausea, fever, rash, and eosinophilia) and not deemed related to other diseases (eg, vomiting or nausea triggered by cluster headache)
- any increase in ALT or AST to levels  $\geq 5$  but  $<8 \times$  the ULN, which is persistent for  $\geq 2$  weeks of repeated measurements
- any increase in ALT or AST to levels  $\geq 8 \times$  the ULN
- in any case where monitoring of liver enzymes cannot be performed according to the protocol guidance

**Follow-Up of Liver Enzymes After Stopping Rules Are Met**

- A patient who meets the above criteria for discontinuation of the IMP should be invited to the investigational site to return the IMP. Early withdrawal visit activities should be performed as soon as possible.
- Liver enzymes should be monitored until normalization or stabilization of the abnormality, according to the discretion of the investigator.
- In any case, following the early withdrawal visit, the minimal follow-up period will be 30 days and will include measurement of liver enzymes at least once weekly (may be performed in local laboratory, with at least 1 test being sent to the central laboratory).
- Every effort should be made to complete the additional tests/evaluations, as described above.

## APPENDIX K. CLINICAL CRITERIA FOR DIAGNOSING ANAPHYLAXIS

As detailed by [Sampson et al 2006](#), anaphylaxis is broadly defined as, “a serious allergic reaction that is rapid in onset and may cause death.” Diagnostic criteria defined by the National Institute of Allergy and Infectious Disease/Food Allergy and Anaphylaxis Network during the second symposium on the definition and management of anaphylaxis, modified from [Sampson et al 2006](#), are as follows:

Anaphylaxis is highly likely when any 1 of the following 3 criteria is fulfilled:

1. Acute onset of an illness (minutes to several hours) with involvement of the skin, mucosal tissue, or both (eg, generalized hives, pruritus or flushing, swollen lips-tongue-uvula) and at least 1 of the following:
  - a. respiratory compromise (eg, dyspnea, wheeze-bronchospasm, stridor, reduced peak expiratory flow [PEF], hypoxemia)
  - b. reduced blood pressure or associated symptoms of end-organ dysfunction (eg, hypotonia [collapse], syncope, incontinence)
2. Two or more of the following that occur rapidly after exposure to a *likely allergen for that patient* (minutes to several hours):
  - a. involvement of the skin-mucosal tissue (eg, generalized hives, itch-flush, swollen lips-tongue-uvula)
  - b. respiratory compromise (eg, dyspnea, wheeze-bronchospasm, stridor, reduced PEF, hypoxemia)
  - c. reduced blood pressure or associated symptoms (eg, hypotonia [collapse], syncope, incontinence)
  - d. persistent gastrointestinal symptoms (eg, crampy abdominal pain, vomiting)
3. Reduced blood pressure after exposure to *known allergen for that patient* (minutes to several hours):
  - a. adults: systolic blood pressure of <90 mm Hg or >30% decrease from that person’s baseline

In the event of suspected anaphylaxis, vital signs, including oxygen saturation and respiration rate, will be measured. Other assessments will be performed at the discretion of the investigator. As a precaution, each investigational site should have a resuscitation cart nearby.

## APPENDIX L. TOTAL BLOOD VOLUME

The total blood volume to be collected for each patient in this study is approximately 131.5 mL (at maximum) for scheduled tests. An additional 30 mL of blood may be collected in the event of follow up for liver enzymes as detailed in [Appendix J](#).

### Total Blood Volumes

Type of samples	Volume per sample (mL)	Total number of samples	Total volume (mL)
Serum chemistry	3.5	5	17.5
Serum pregnancy a	3.5	2	7
Hematology	2	5	10
Coagulation	4.5	5	22.5
FSH b	3.5	1	3.5
Pharmacokinetics	4	4	16
ADA c	5	3	15
Biomarker Serum	8.5	2	17
Biomarker Plasma	6	2	12
Biomarker RNA	2.5	2	5
Pharmacogenomic d	6	1	6
Total	--	32	131.5

a A serum pregnancy test will be performed for women of childbearing potential at screening only.

b Postmenopausal women only.

c ADA assessment will also be collected upon observation of severe hypersensitivity or anaphylaxis or if there is a suspected causal relationship of an adverse event potentially being related to immunogenicity (eg, lack of efficacy).

d Unless the patient declines testing or local regulations prohibit testing.

ADA=antidrug antibody; FSH=follicle-stimulating hormone; RNA=ribonucleic acid.

## APPENDIX M. CLINICAL LABORATORY TESTS

### Clinical Laboratory Tests

Serum Chemistry	Hematology and Coagulation	Urinalysis
Calcium	Hemoglobin	Color and appearance
Phosphate	Hematocrit	Protein
Sodium	Erythrocytes	Glucose
Potassium	Platelets	Albumin
Chloride	Leucocytes	Ketones
Magnesium	– Neutrophils	Leukocyte esterase
Creatinine	– Lymphocytes	Nitrite
Glucose	– Eosinophils	Bilirubin
Blood urea nitrogen (BUN)	– Monocytes	Hemoglobin
Alanine aminotransferase (ALT)	– Basophils	pH
Aspartate aminotransferase (AST)	Lymphocytes atypical	Specific gravity
Lactate dehydrogenase (LDH)	Prothrombin International Normalized Ratio (INR)	Microscopic tests
Gamma-glutamyl transpeptidase (GGT)		– Bacteria
Alkaline phosphatase		– Erythrocytes
Bicarbonate		– Leucocytes
Carbon dioxide		– Crystals
Protein		– Casts
Albumin		
Bilirubin		
Direct bilirubin		
Indirect bilirubin		

ALP=alkaline phosphatase; ALT=alanine aminotransferase; AST=aspartate aminotransferase; GGT=gamma-glutamyltranspeptidase; INR=international normalized ratio; RBC=red blood cell; WBC=white blood cell.

## **APPENDIX N. PHARMACOKINETICS SAMPLES**

### **Specimen Sampling and Handling**

For plasma collection, samples will be collected in anticoagulant tubes, inverted slowly 6 to 8 times to mix the contents, and placed on water/ice (approximately 4°C). Blood samples will be centrifuged (1500 g, approximately 10 minutes, at 2 to 8°C) between 5 minutes and 1 hour after sampling. If a refrigerated centrifuge is not available, samples should be chilled before centrifugation. Other measures should be taken as appropriate to prevent samples from heating significantly during centrifugation. Separated plasma will be transferred in approximately equal portions in 2 labeled 2 mL-polypropylene tubes (Sets A and B).

Labels for samples should include study number, patient randomization number, nominal collection time (Visit number), Set A or B, and indication that they are pharmacokinetic samples. Samples will be stored at a temperature of –70°C to –20°C (inclusive) in an upright position until they are shipped to the central laboratory.

### **Shipment and Analysis of Samples**

Plasma samples for all patients will be shipped from the investigational center to the central laboratory, where they will be stored until shipped to the sponsor or designee for analysis. Samples will be stored in an upright position at –70°C until assayed. The central laboratory will be notified before the shipment of the samples and will be sent the shipping information when the samples are shipped. An electronic file containing sample demographics will be emailed to the bioanalytical laboratory and the sponsor's representatives from bioanalytical departments for each shipment.

Set A samples will be transported frozen, with a temperature data logger and with dry ice sufficient for 4 days, on a monthly basis to the central laboratory. Central laboratory will ship the Set A samples on a monthly basis to the bioanalytical laboratory with dry ice sufficient for 4 days and with a temperature data logger.

Set B samples will be sent to the same laboratory as that for Set A. Instructions as to the disposition of the Set B samples will be provided by the sponsor. Sample shipments should be sent no later in the week than Wednesday morning for next-day delivery. Samples are not to arrive on the weekend.

Samples will be analyzed using an appropriate validated method. Timing of the initiation of sample analysis will be determined by the sponsor's representatives of bioanalytical departments responsible for the bioanalysis while keeping the study blinding, if any, intact.

